2.4.4 Analyses of efficacy endpoints

If efficacy at the interim analysis is demonstrated for the primary endpoint of annualized rate of moderate and severe COPD exacerbations over the 52-week treatment period with an alpha as determined in [Table 9](#) (see [Section 3](#)):

- All data up to the time of the interim analysis cut-off date will be used in the inferential analyses for the event type endpoints including the primary endpoint and time to event endpoints (up to the cut-off date), and the change from baseline in pre-BD FEV1 at Week 12 endpoints (both the ITT population and the baseline FeNO ≥ 20 ppb subgroup).
- For Week 52 endpoints, only participants who have the opportunity to reach Week 52 assessments at the time of the IA cut-off date (ie, completed the Week 52 study period or would have completed had they not discontinued) will contribute to the inferential analyses for the continuous and proportion type endpoints at Week 52 and by visit.

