If patients withdraw from the study before Visit 16 (Week 52), moderate or severe exacerbation events that may occur after study discontinuation will not be observed. These patients are considered as patients with missing data on moderate or severe exacerbation. Number of patients with missing data, reasons and timing for patient withdrawals will be summarized by treatment groups. Summary statistics of selected demographic and baseline disease characteristics will be provided for patients with missing data and patients with complete data separately. In addition, the following sensitivity analyses will be conducted to assess the robustness of the conclusion based on the primary analysis.

Pattern mixture model - multiple imputation (PMM-MI)

For each patient with missing data of moderate or severe exacerbation events, individual bi-weekly event probability will be estimated using observed data with adjustment of the planned treatment group, region (pooled country), ICS dose at baseline (high dose ICS [yes/no]), smoking status at screening (current smokers or not), baseline disease severity (as % predicted post-bronchodilator FEV₁), and number of moderate or severe COPD exacerbation events within one year prior to the study (≤ 2 , 3, or ≥ 4). The total number of AECOPD moderate or severe events (on bi-weekly basis) will be calculated based on data imputed using multiple imputation.

Control-based PMM-MI

For each patient with missing data of moderate or severe exacerbation events, individual bi-weekly event probability will be estimated using observation in the placebo arms only, with adjustment of region (pooled country), ICS dose at baseline (high dose ICS [yes/no]), smoking status at screening (current smokers or not), baseline disease severity (as % predicted post-bronchodilator FEV₁), and number of moderate or severe COPD exacerbation events within one year prior to the study (≤ 2 , 3, or ≥ 4). The total number of AECOPD moderate or severe events (on bi-weekly basis) will be calculated based on data imputed using multiple imputation.

Tipping point analysis

For each patient with missing data of moderate or severe exacerbation events, the bi-weekly event will be imputed in a similar fashion as PMM-MI based on various odds values. If the patient is on dupilumab, the predicted odds will be increased; if the patient is on Placebo, the predicted odds value will be decreased. The adjusted rate will then be used to impute the number of events that

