would occur during the missing observation period. A sequence of increasing/decreasing ratio will be used to generate different imputed datasets.

For each of the above methods, a negative binomial model will be fitted using each of the complete datasets composed of observed and imputed data, including the total number of observed and imputed events during the 52 weeks as the response variable, with the treatment group, region (pooled country), ICS dose at baseline (high dose ICS [yes/no]), smoking status at screening (current smokers or not), baseline disease severity (as % predicted post-bronchodilator FEV₁), and number of moderate or severe COPD exacerbation events within one year prior to the study (≤ 2 , 3, or ≥ 4) as covariates. Log transformed observation duration will be the offset variable for patients who complete the 52-Week treatment/study period, and log transformed 52 weeks will be the offset variable for patients who discontinue the study before Visit 16 (Week 52). SAS MIANALYZE procedure will be used to generate statistical inferences by combining results from the analysis with each dataset using Rubin's formula.

More details of the imputation and analyses methods are provided in Appendix K:

Subgroup analyses

To assess the consistency in treatment effects across different subgroup levels, subgroup analyses will be conducted for the primary efficacy endpoint with respect to:

- Age group (<65, ≥ 65 years; 40-64, 65-74, 75-85)
- Gender (Male, Female)
- Region
- Territory
- Race (White, Non-white)
- Ethnicity (Hispanic or Latino, Not Hispanic or Latino)
- Baseline weight (<70, ≥ 70 - <90, ≥ 90 kg; <60, ≥ 60 kg)
- Baseline BMI (<25, ≥ 25 - <30, ≥ 30 kg/m²)
- ICS high dose level at baseline (High-dose ICS, Non-high-dose ICS, No ICS)
- ICS dose level at baseline (< median, \geq median)
- Smoking status at screening (current smokers, former smokers)
- Number of moderate-or-severe COPD exacerbation events within one year prior to V1 (≤ 2 , 3, or ≥ 4)
- Number of severe COPD exacerbation events within one year prior to V1 (0, 1, ≥ 2 ; 0, ≥ 1)
- Baseline predicted post-bronchodilator FEV₁% (<50%, $\geq 50\%$)
- Baseline pre-bronchodilator FEV₁ (< median, \geq median)
- Baseline FEV₁ reversibility (<12%, $\geq 12\%$; < median, \geq median)
- Baseline fractional exhaled nitric oxide (FeNO) (<20, ≥ 20 ppb)
- Baseline eotaxin-3 (< median, \geq median)
- Baseline IgE (<100, ≥ 100 IU/ml)

- Baseline PARC (< median, \geq median)

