First, missing values will be imputed by PMM-MI as illustrated above. The imputed values in placebo group will then be shifted by adding a sequence of positive values and the imputed values in dupilumab group will be shifted by subtracting a sequence of positive values. For each combination of the shift parameters, each of the imputed and shifted datasets will be analyzed with the ANCOVA model and their results will be combined using Rubin's formula to generate statistical inference. LS mean difference between dupilumab and placebo in change from baseline in pre-BD FEV₁ at Week 12 and the corresponding p-values will be provided for each combination of shift parameters.

More details of the imputation and analyses methods are included in Appendix K.

2.4.4.2.2 Analysis of the change from baseline in pre-bronchodilator FEV₁ and SGRQ total score and domain scores at Week 52 for dupilumab versus placebo

The change from baseline in pre-bronchodilator FEV₁ at Week 52 will be analyzed in a similar way as change from baseline in pre-bronchodilator FEV₁ at Week 12 and the model will include values up to Week 52 as response variables. The analysis will be performed in the full ITT population and also in the baseline FeNO ≥ 20 ppb subgroup.

The change from baseline in SGRQ total score and domain scores at Week 52 will be analyzed in a similar way as change in pre-bronchodilator FEV₁ at Week 52 except that the MMRM model will include the following covariates: treatment group, region (pooled country), ICS dose at baseline (high dose ICS [yes/no]), smoking status at screening (current smokers or not), visit, treatment-by-visit interaction, baseline SGRQ total score, and SGRQ baseline-by-visit interaction.

Descriptive statistics including number of patients, mean, standard error, and least squares (LS) means will be provided. In addition, difference in LS means and the corresponding 95% confidence intervals (CI) will be provided along with the p-values.

2.4.4.2.3 Analysis of proportion of patients with SGRQ improvement ≥ 4 points at Week 52 dupilumab versus placebo

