2.4.4.3 Multiplicity issues

Multiplicity is considered for performing an interim analysis and for testing multiple endpoints. The overall Type-I error rate will be controlled at the two-sided 0.05 level.

An interim analysis will be performed using the Kim-DeMets (9) spending function when the information fraction is ≥ 0.92 based on follow-up time for the primary endpoint of annualized rate of moderate or severe COPD exacerbations over 52-week treatment period (see [Section 3](#)).

A hierarchical testing procedure will be used for testing primary, key secondary and other endpoints. If the primary endpoint does not demonstrate efficacy at this interim analysis then the study will remain blinded and the primary endpoint will be retested at the 52-week final analysis time point with an $\alpha=0.049$. If the primary endpoint demonstrates efficacy at this interim analysis based on the alpha allocated, then the rest of the multiplicity-controlled endpoints will be tested with $\alpha=0.05$. The comparisons will be tested based on the hierarchical order below.

1) Primary efficacy endpoints:

- Annualized rate of moderate or severe COPD exacerbations over the 52-week treatment period compared to placebo.

2) Secondary/exploratory efficacy endpoints:

- Change in pre-bronchodilator FEV₁ from baseline to Week 12 compared to placebo
- Change in pre-bronchodilator FEV₁ from baseline to Week 52 compared to placebo
- Change in pre-bronchodilator FEV₁ from baseline to Week 12 compared to placebo in the subgroup of patients with baseline FeNO ≥ 20 ppb
- Change in pre-bronchodilator FEV₁ from baseline to Week 52 compared to placebo in the subgroup of patients with baseline FeNO ≥ 20 ppb
- Change from baseline to Week 52 in SGRQ total score compared to placebo
- Proportion of patients with SGRQ improvement ≥ 4 points at Week 52 compared to placebo
- Change in E-RS COPD total score from baseline to Week 52 compared to placebo
- Annualized rate of moderate or severe COPD exacerbation compared to placebo over the 52-week treatment period in the subgroup of patients with baseline FeNO ≥ 20 ppb

The study is considered positive when the primary endpoint achieves statistical significance.

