3 INTERIM ANALYSIS

An interim analysis is planned when the information fraction is ≥ 0.92 based on follow-up time for the primary endpoint of annualized rate of moderate or severe COPD exacerbations over a 52-week treatment period. The information fraction at the time of interim analysis will be estimated using a conservative approach assuming all ongoing patients complete the 52-week treatment period. All participants will have complete follow-up for the key secondary endpoint of change from baseline in FEV₁ at Week 12. The purpose of this interim analysis is to potentially demonstrate efficacy when $\geq 92\%$ of the information fraction for the primary endpoint is available, but prior to all patients completing the 52-week treatment period, as COPD is a disease with a high unmet medical need.

To control the overall type I error at $\alpha=0.05$, the Kim DeMets approach (9) will be used with the power parameter rho (ρ) determined based on the information fraction observed at the time of the interim analysis and to maintain an $\alpha=0.049$ at the final analysis (Table 9). The details of the hierarchical testing strategy at interim analysis and final analysis are specified in Section 2.4.4.3.

Table 9 - Kim-DeMets alpha spending function to control the overall alpha at 0.05

Information fraction	Rho (ρ)	α at interim analysis	α at final analysis
0.92 to <0.93	12	0.018	0.049
0.93 to <0.94	12	0.020	0.049
0.94 to <0.95	13	0.022	0.049
0.95 to <0.96	14	0.024	0.049
0.96 to <0.97	15	0.027	0.049

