4 DATABASE LOCK

The database lock for primary analysis is planned based on the results of the interim analysis (see more details in [Section 3](#)).

If efficacy at the interim analysis is not demonstrated, the database lock for the primary analysis will be planned based on the date when the last patient completes the Week 52 visit or discontinues from the study before Week 52. Analyses will be based on all data collected up to this database lock and will be considered as the final analysis of the CSR. Additional data between this database lock and last patient completing last visit will be summarized in a CSR addendum.

If efficacy at the interim analysis is demonstrated, then the interim analysis database lock will be considered the primary analysis for all endpoints. The database lock for final analysis is planned when all patients complete the Week 52 visit or discontinue from the study before Week 52 but may occur when all patients complete the Week 64 visit or discontinue from the study.

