For each patient who early withdraws from the study, 40 sets of complete event count data can be obtained by summing the observed event count prior to withdrawal and each series of imputed binary events after withdrawal up to Week 52.

Step 4. A negative binomial model with the same set of covariates as in the primary analysis will be fitted to the 40 sets of complete datasets obtained in Step 3, so as to obtain 40 sets of treatment effect estimates and p-values accordingly. Log transformed observation duration will be the offset variable for patients who complete the 52-Week treatment/study period, and log transformed 52 weeks will be the offset variable for patients who discontinue the study before Visit 16 (Week 52). Then, the SAS MIANALYZE procedure will be used to generate statistical inferences by combining results from the 40 analyses using Rubin's formula.

Step 2, 3 and 4 will be repeated iteratively until the p-value for combined treatment effect of dupilumab compared to placebo estimated in Step 4 is >0.05 or the maximum applicable treatment effect has been reached.

Change from baseline in pre-BD FEV₁ at Week 12

- ***Pattern mixture model-multiple imputation (PMM-MI)***

Step 1. Monotone missing pattern was induced by Markov Chain Monte Carlo (MCMC) method using PROC MI: for patients who have missing values at intermediate visits, but have value at subsequent visits, the intermediate missing values were imputed assuming a multivariate normal distribution over observations from all visits. 40 datasets with a monotone missing pattern will be obtained using this method.

Step 2. For each of the imputed dataset with monotone missing pattern obtained in Step 1, the remaining missing data will be imputed using the regression method for the monotone pattern with adjustment for covariates including treatment groups, age, sex, height, region (pooled country), ICS dose at baseline (high dose ICS [yes/no]), smoking status at screening (current smokers or not), and baseline pre-BD FEV₁. All available data in the monotone missing pattern data will be used. 40 fully imputed datasets are obtained.

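### After success at the interim (alpha 0.018 to 0.027), the primary-endpoint tipping point is still set at p>0.05, which overstates robustness

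*SAP*

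**What the plan says.** SAP 2.4.4.1 gives the purpose of the missing-data analyses: "sensitivity analyses will be conducted to assess the robustness of the conclusion based on the primary analysis". One of them is a tipping point analysis on the bi-weekly event odds, raised for dupilumab and lowered for placebo. For the grid, the section says only this: "A sequence of increasing/decreasing ratio will be used to generate different imputed datasets". Appendix K sets the end of the search. The shift, imputation and pooling steps are repeated "until the p-value for combined treatment effect of dupilumab compared to placebo estimated in Step 4 is >0.05", or until a maximum effect that is not quantified has been reached. The rule does not distinguish interim from final analysis.

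The criterion for the primary endpoint does depend on the analysis:

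- SAP 2.4.4 has the endpoint tested at the interim "over the 52-week treatment period with an alpha as determined in" Table 9.
- Table 9 in SAP section 3 ("Kim-DeMets alpha spending function to control the overall alpha at 0.05") lists interim levels of 0.018, 0.020, 0.022, 0.024 and 0.027 by information fraction, and 0.049 at the final analysis. Protocol Table 12 is the same.
- SAP 2.4.4.3 begins its success branch with "If the primary endpoint demonstrates efficacy at this interim analysis based on the alpha allocated" and gives alpha 0.05 to the remaining endpoints in the hierarchy.
- SAP section 4 covers the same branch: "then the interim analysis database lock will be considered the primary analysis for all endpoints".

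**The concern.** A tipping point states how far the missing-data assumption must be pushed before the conclusion fails. After interim success, the conclusion is rejection at 0.018 to 0.027. A scenario with a pooled p-value of 0.035 fails that criterion, yet the Appendix K rule passes over it and keeps searching. The reported tipping point is then a larger departure than the one at which the declared significance is lost, and the error always favours the trial.

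A reader may also be unable to correct for this. For Week 12 FEV1, SAP 2.4.4.2.1 promises that "corresponding p-values will be provided for each combination of shift parameters". The primary-endpoint text in 2.4.4.1 and Appendix K makes no such promise, so the point where the Table 9 level is crossed may not appear in the output.

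**Working it through.** **Inputs.** SAP 1.3: placebo rate 1.5 per year, dispersion 1, 462 patients per arm, mean follow-up 0.95 year, planned rate ratio (RR) 0.75. SAP Table 9: information fractions, rho and alphas.

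**The plan's own figures.** Spending 0.05 × t^rho at the lower end of each band gives 0.01838, 0.02093, 0.02237, 0.02438 and 0.02710. Cut to three decimals, these are the Table 9 values. For power, SE² = (1/462) × [1/(0.95 × 1.5) + 1 + 1/(0.95 × 1.125) + 1], so SE = 0.0887. Then Φ(0.2877/0.0887 − 1.960) = 0.900, the stated 90%.

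**Distance between the thresholds.** The two-sided boundaries are |z| = 2.366, 2.326, 2.290, 2.257 and 2.212, against 1.960 at p=0.05. The search therefore runs 0.25 to 0.41 z-units past the efficacy boundary.

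**Rate ratio scale.** Take SE² = (1/462) × [1/(1.5T) + 1 + 1/(1.5T × RR) + 1] with T = 0.95t (follow-up shortened evenly) and solve −ln(RR)/SE for each threshold.

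| t | Interim alpha | RR at interim boundary | RR at p=0.05 | Z at RR 0.75 | Φ(Z − boundary) |
|---|---|---|---|---|---|
| 0.92 | 0.018 | 0.809 | 0.840 | 3.181 | 0.79 |
| 0.96 | 0.027 | 0.822 | 0.841 | 3.212 | 0.84 |

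If information is instead taken as proportional to t, the boundary ratios are 0.805 to 0.820, p=0.05 falls at 0.836 to 0.839, and the probability of interim success is 0.77 to 0.83.

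**Odds scale (illustration).** The documents give neither the shift grid nor the withdrawals. Assume that a fraction m of follow-up is imputed, with the dupilumab odds multiplied and the placebo odds divided by the same k.

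1. The bi-weekly event probability is p = rate/26 and the odds are o = p/(1 − p).
2. The shifted odds o′ give an imputed rate q = 26 × o′/(1 + o′).
3. The arm's average rate is R = (1 − m) × rate + m × q.
4. Solve for k so that Z = −ln(R1/R0)/√{(1/462) × [1/(t × R0) + 1 + 1/(t × R1) + 1]} equals each threshold, where R1 is dupilumab and R0 placebo.

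Example with m = 5%, t = 0.92, RR 0.75 and k = 2.14: R0 = 0.95 × 1.5 + 0.05 × 0.723 = 1.461 and R1 = 0.95 × 1.125 + 0.05 × 2.294 = 1.183. The ratio is 0.810 and Z is 2.37, the boundary for 0.018.

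| Missing time | Interim alpha | k at interim alpha | k at p=0.05 | Excess |
|---|---|---|---|---|
| 5% | 0.018 | 2.14 | 2.91 | 36% |
| 5% | 0.027 | 2.46 | 2.95 | 20% |
| 10% | 0.018 | 1.49 | 1.78 | 20% |
| 10% | 0.027 | 1.61 | 1.80 | 12% |

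Over observed ratios of 0.70 to 0.78, the excess runs from about 10% to 41%.

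**Simulation check.** There were 300 trials per case, with negative binomial counts, staggered interim follow-up, 40 imputations, Rubin pooling and no covariates. Among successful interims, the median ratio of the two k values was 1.32 and 1.17 (5% missing; alpha 0.018 and 0.027) and 1.22 and 1.13 (10% missing). Interim success occurred in 235 to 240 of 300 trials.

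**The case against.** The best defence is that Appendix K states when to stop searching, not how to report. A grid stepped outward to p>0.05 has already passed the interim boundary, and a pooled p-value exists at every step. A nominal 0.05 is also conventional: it marks where the 95% confidence interval for the rate ratio, which the SAP reports in either branch, would reach 1. No pass/fail rule hangs on the tipping point, and the protocol says only that such analyses may be included. If the search first meets its unquantified maximum, before the interim boundary, both thresholds give the same answer.

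Most of this is true and limits the weight of the point. It does not remove it. In an analysis of this kind the tipping point is where the search stops, and printing the intermediate p-values is promised only for FEV1. The 95% interval is not the criterion on which interim efficacy would be declared.

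The size can also be challenged. Appendix K shifts the odds by an amount, 2.4.4.1 speaks of a ratio, and neither fixes symmetry between arms. At 5% missing time and a ratio of 0.75, the unshifted odds ratio is 0.739. The two shifts then put dupilumab dropouts at 0.739 × 2.14² = 3.4 and 0.739 × 2.91² = 6.3 times the placebo odds; both are extreme, and the qualitative reading would not change. It could change for a result nearer the boundary. At an observed ratio of 0.80, 5% missing time and t = 0.95 (information proportional to t), k is 1.25 at p=0.024 and 1.64 at p=0.05. With an unshifted odds ratio of 0.790, those are 1.2 and 2.1 times the placebo odds. Finally, the 77% to 84% chance of interim success holds at a true ratio of 0.75; at 0.80, with even follow-up, it is about 55% to 62%.

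**Conclusion.** The concern holds. In the interim-success branch, the Appendix K threshold does not match the criterion on which the primary endpoint would be declared significant, and nothing in the SAP adapts it. Under the planning inputs, rate ratios between about 0.81 or 0.82 and 0.84 would count as not tipped although the interim criterion is no longer met. This is the more likely branch under the sponsor's own assumptions. The excess on the odds scale, about 10% to 41%, is an illustration resting on a symmetric multiplicative shift, 5% or 10% missing time and observed ratios of 0.70 to 0.78.

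The mismatch concerns a supportive analysis and should be corrected, but it does not threaten the primary inference. The 0.05 limit for Week 12 FEV1 is consistent with SAP 2.4.4.3 in this branch and needs no change.

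**What to change.** In Appendix K, for the primary endpoint only, define the tipping point as the first shift at which the pooled p-value exceeds the level at which the endpoint was declared significant: the applicable Table 9 interim alpha, or 0.049 at the final analysis. State in the SAP that the pooled p-value will be reported at every shift, as is already planned for FEV1. The search can still run on to p>0.05, with that crossing shown as additional information.

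The change should be made before the interim database lock, so that the threshold is not chosen with results in hand. It costs one or two SAP sentences and one program parameter, needs no new data and leaves the primary test as it is. The downside is that, after interim success, the reported tipping point will look less favourable.

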Appendix L Summary of primary estimands for main endpoints

Endpoint Category	Estimands			
	Endpoint(s) ^a	Population	Intercurrent event(s) handling strategy and missing data handling	Population-level summary
Primary objective: The primary objective of this study is to evaluate the efficacy of dupilumab 300 mg every 2 weeks compared to placebo in reducing annualized rate of acute moderate or severe COPD exacerbation (AECOPD) over the 52-week treatment period in patients with moderate or severe COPD.				
Primary endpoint – Event	Annualized rate of AECOPD exacerbation events over the 52-week treatment period.	ITT	
The intercurrent events will be handled as follows:
 
 Discontinuation of study treatment before Week 52: Off-study treatment data up to Week 52 will be included in the analysis (treatment policy strategy). 
In addition, the missing data imputation rules are as follows:
 
 Discontinuing the study follow-up before Week 52: Analyses will be censored at the time of study discontinuation. 	Negative binomial regression model using the total number of events occurred during the 52-week planned treatment period as the response variable, with the treatment group, region (pooled country), ICS dose at baseline, smoking status at screening, baseline disease severity, and number of moderate or severe COPD exacerbation events within one year prior to the study as covariates. Log-transformed observation duration will be used as offset variable.
Secondary objective: To demonstrate the efficacy of dupilumab on spirometry and health related quality of life endpoints, separately, at various time points or population				
Secondary endpoint – Continuous	Change from baseline in FEV ₁ at Week 12 Change from baseline in FEV ₁ at Week 52 Change from baseline in SGRQ at Week 52 Change from baseline in E-RS at Week 52 ^b	ITT (For FEV ₁ endpoints, also patients with baseline FeNO ≥ 20 ppb)	
The intercurrent events will be handled as follows:
 
 Discontinuing the study intervention prior to Week 12 or Week 52: all data collected after discontinuation will be used in the analysis (treatment policy strategy). 
In addition, the missing data imputation rules are as follows:
 
 Missing data will be imputed latently by MMRM based on missing at random assumption 	MMRM model using change from baseline in corresponding endpoint values up to corresponding weeks as response variables, and factors for treatment group, age, sex, height (age, sex and height are only included for spirometry endpoints analyses), region (pooled country), ICS dose at baseline, smoking status at screening, visit, treatment-by-visit interaction, baseline value of the endpoint, and baseline-by-visit interaction as covariates.

Endpoint Category	Estimands			
	Endpoint(s) ^a	Population	Intercurrent event(s) handling strategy and missing data handling	Population-level summary
Secondary endpoint – Proportion	Proportion of SGRQ improvement (≥ 4 points) at Week 52.	ITT	
The intercurrent events will be handled as follows:
 
 Discontinuation of study intervention prior to Week 52: Off-study intervention data will be included in the analysis (treatment policy strategy). 
In addition, the missing data imputation rules are as follows:
 
 Having missing data at Week 52: Participants will be considered as non-responders. 	Logistic regression model, with treatment group, region (pooled country), ICS dose at baseline, smoking status at screening, and baseline SGRQ total score as covariates
Secondary objective: To evaluate the effect of dupilumab on moderate and severe COPD exacerbations				
Secondary endpoint – Time-to-event	Time to AECOPD exacerbation events during the 52-week treatment period	ITT	
The intercurrent events will be handled as follows:
 
 Discontinuation of study intervention before Week 52: Off-study intervention data up to Week 52 will be included in the analysis (treatment policy strategy). 
In addition, the missing data imputation rules are as follows:
 
 Discontinuing the study follow-up before Week 52: Analyses will be censored at the time of study discontinuation 	Cox proportional hazards model using the time to the first event as the dependent variable, and treatment group, region (pooled country), ICS dose at baseline, smoking status at screening, baseline disease severity, and number of moderate or severe COPD exacerbation events within one year prior to the study as covariates

a Additional secondary objectives/endpoints are not included in this table but would be handled with a similar strategy as the endpoint type (ie, Continuous, proportion, event, time-to-event) at other weeks.

b Exploratory endpoint
